5.2 SAFETY ANALYSIS SET

The Safety Analysis Set (SAF) consists of all patients with informed consent who received at least one dose of abrocitinib.

This population will be used for safety analysis, i.e. for the analysis of adverse events and laboratory values.

5.3 OTHER ANALYSIS SET

The modified Full Analysis Set (mFAS) consists of all patients who met the eligibility criteria, received at least one dose of abrocitinib and had at least one post-baseline visit. This population will be used for analysis of primary and secondary endpoints, if $\geq 10\%$ of the FAS is omitted.

The Per Protocol Set (PP) consists of all patients who met the eligibility criteria, received at least one dose of abrocitinib and completed all visits, irrespective of the time-window.

This population will be used for analysis of primary and secondary endpoints, if $\geq 10\%$ of the mFAS is omitted.

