EASI	X	X	X	X	X	X

Study period based on routine visits	Baseline (Enroll ment)	Month 1	Month 3	Month 6	Month 9	Month 12 End of Study (EoS)
IGA	X	X	X	X	X	X
Pruritus-NRS	X	X	X	X	X	X
PP-NRS	X	X	X	X	X	X
DLQI	X	X	X	X	X	X
POEM	X	X	X	X	X	X
MOS	X	X	X	X	X	X
PBI	X	X	X	X	X	X
EQ-5D-5L	X	X	X	X	X	X
HADS	X	X	X	X	X	X

^{*} This includes patients who discontinued treatment with abrocitinib.

Figure 1. Timelines

The planned observation period of each patient is 12 months. In this time period up to 6 visits will be documented.

Figure 2. Study Period

Table 2. Definition of time windows for study visits

In order to collect comparable study data, Visits 1 to 3 occurring ± 14 days and Visits 4 to 6 occurring ± 28 days of the scheduled visit date will be used for data analysis (interim analysis).

Visit Label	Target Day	Definition [Day window]
Enrolment	1	1
Month 1	30	16 to 44
Month 3	91	77 to 105
Month 6	182	154 to 210
Month 9	273	245 to 301
Month 12	365	337 to 393

Visits that do not meet the defined windows as displayed in the table above will also be included in the final analysis and clinical study report. Therefore, all visits will be included using the visit time slots shown below. If more than one visit appears in a 3-month window, only the visit closest to the target day will be respected.

Amended definition:

Visit designation	Target Day	Definition [Day window]
Enrolment	1	1
Month 1	30	2 to 44
Month 3	91	45 to 105
Month 6	182	106 to 210
Month 9	273	211 to 301
Month 12	365	302 to 393

However, for analysis of safety parameters, all AEs/SAEs documented within the applicable reporting period will be analyzed.

- For the lab values, if the calculated study day for the labelled baseline visit is not study Day 1, but falls within 40 days before the start of the study dosing, then that data should be used for the baseline instead of leaving baseline missing.
- For the other values, if the calculated study day for the labelled baseline visit is not study Day 1, but falls before the start of the study dosing, then that data should be used for the baseline instead of leaving baseline missing.
- If baseline is missing there will be no imputation and although the subject's data will be included in summary data it will not be included in any change from baseline analyses.

If two or more routine visits fall into the same window, keep the one closest to the Target Day. If two routine visits are equal distance from the Target Day in absolute value, the later visit should be used.

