5 ANALYSIS SETS/POPULATIONS

5.1 FULL ANALYSIS SET

The Full Analysis Set (FAS) consists of all patients with informed consent who met the eligibility criteria and received at least one dose of abrocitinib. This population will be used for all analyses except safety.

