7 HANDLING OF MISSING VALUES

In general, no imputation of missing data will be performed. Exceptions are described below. For categorical variables the number of missing values will be displayed in the respective tables. For at least interval-scaled variables the number of available observations will be displayed.

Incomplete dates will be handled as follows, if not specified otherwise:

If the day of a date is missing then the day is set to the 15th of the respective month. If day and month are missing then the date will be set to the middle of the respective year (in case of the year of the data cut: middle of time from beginning of year to data cut).

Missing values in PRO will be replaced according to the respective manual.

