8 STATISTICAL METHODOLOGY AND STATISTICAL ANALYSES

8.1 STATISTICAL METHODS

All parameters will be evaluated in a descriptive respective explorative manner. Binary, categorical and ordinal parameters will be summarized by means of absolute and percentage numbers within the various groups (including 'missing data' as valid category). Those variables will be compared for the subgroups in an explorative manner using Chi-Square test respective Fisher's exact test if a sample size of at least 30 in each subgroup is not reached. Numerical data will be summarized by means of standard statistics (i.e. number of available data, number of missing data, mean, standard deviation, minimum, median and maximum) and compared exploratively for the subgroups by Mann-Whitney-U-test. Due to the descriptive/explorative manner of the analysis no adjustment for multiple testing will take place. Graphical displays may be used.

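### With missing values excluded, the mFAS analysis triggered by 10% loss repeats the FAS Month 3 rates, and SAP 8.1 and 8.2.3 disagree on the denominator

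*SAP*

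**What the plan says.** SAP 5.1 defines the FAS as "all patients with informed consent who met the eligibility criteria and received at least one dose of abrocitinib". SAP 5.3 forms the mFAS from eligible patients who "received at least one dose of abrocitinib and had at least one post-baseline visit", which adds one condition to the FAS, and applies it to primary and secondary endpoints if 10% or more "of the FAS is omitted". The same section defines a Per Protocol set of patients who "completed all visits, irrespective of the time-window", used if 10% or more of the mFAS is lost in turn.

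Three places bear on how a missing Month 3 value is treated:

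- SAP 8.2.3 lists FAS, mFAS and PP for both Month 3 responses and marks missing data as excluded. The other primary and secondary rows carry the same entry.
- SAP 7 states: "In general, no imputation of missing data will be performed". It adds: "For categorical variables the number of missing values will be displayed in the respective tables".
- SAP 8.1 summarises binary, categorical and ordinal variables by "absolute and percentage numbers within the various groups (including 'missing data' as valid category".

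For a patient without a baseline value, SAP 1.1 says that although the data enter the summaries, "it will not be included in any change from baseline analyses". The SAP does not say whether 8.1 or 8.2.3 sets the denominator of the Month 3 percentages.

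**The concern.** A set that comes into use only when a tenth or more of the FAS has no follow-up looks like a planned response to early loss. Such loss is plausible here, since both documents say that no visit is mandatory. Protocol 9.9 also acknowledges that an as-observed analysis can be biased by missing outcomes, and more so as their number grows.

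If the triggered analysis drops only patients whom the FAS analysis has already dropped, it yields a second table with the same figures under a different label. The study's main output is two Month 3 percentages. What is at stake is whether a reader can see how sensitive they are to patients who never came back, and whether two programmers working from this SAP would compute the same percentage.

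**Working it through.** The documents state no response rate, loss rate or precision target, so there is no plan figure to reproduce. The check is denominator arithmetic.

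**Inputs from the documents.** The FAS and mFAS definitions and the 10% trigger (SAP 5.1, 5.3); exclusion of missing data (8.2.3); missing as a category (8.1); no imputation (7); planned enrolment of at least 750 (Protocol 9.5). Signed consent is itself an inclusion criterion (Protocol 9.2.1), so the mFAS is a subset of the FAS.

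**Assumptions, not in the documents.** All 750 enter the FAS; 10% or 20% have no post-baseline visit; 0% or 10% of the mFAS also lack a Month 3 value; response among those observed is about 30%, 50% or 70%. Counts are rounded to whole patients.

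**Notation.** N = FAS size; m = FAS patients with no post-baseline visit; n = patients with an evaluable Month 3 value; R = responders among those n.

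**Step 1, rule in 8.2.3 (missing excluded).** Every patient counted in n has a post-baseline visit and so belongs to both sets.

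- FAS rate = R/n and mFAS rate = R/n, whatever the values of N, m and the response rate.
- A patient with no baseline EASI leaves EASI-75 in both sets alike, so the identity still holds.

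**Step 2, rule in 8.1 (missing as a category in the percentage base).**

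- FAS rate = R/N and mFAS rate = R/(N − m).

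**Step 3, range over all FAS patients.**

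- Lower bound (missing = non-response) = R/N.
- Upper bound (missing = response) = (R + N − n)/N.

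| m | n | R | 8.2.3: FAS and mFAS | 8.1: FAS | 8.1: mFAS | All-FAS range |
|---|---|---|---|---|---|---|
| 75 (10%) | 675 | 202 | 29.9% | 26.9% | 29.9% | 26.9% to 36.9% |
| 75 (10%) | 675 | 338 | 50.1% | 45.1% | 50.1% | 45.1% to 55.1% |
| 75 (10%) | 675 | 472 | 69.9% | 62.9% | 69.9% | 62.9% to 72.9% |
| 75 (10%) | 608 | 304 | 50.0% | 40.5% | 45.0% | 40.5% to 59.5% |
| 150 (20%) | 600 | 300 | 50.0% | 40.0% | 50.0% | 40.0% to 60.0% |

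Second row in full: 338/675 = 50.1%; 338/750 = 45.1%; (338 + 750 − 675)/750 = 413/750 = 55.1%.

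**Step 4, numerical scores.** An absent EASI, SCORAD, DLQI or POEM score cannot enter a mean, median or percentage change. Post-baseline summaries of such scores are therefore the same in FAS and mFAS under either rule. Baseline summaries can differ, because the lost patients do have baseline values.

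**Step 5, the PP set.** Its Month 3 rates can differ from those of the other two sets, but it keeps only patients who completed every visit. It moves further from the patients lost early.

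**The case against.** The strongest reply is SAP 8.1. IGA 0/1 and EASI-75 at Month 3 are binary. If 8.1 sets the percentage base, the FAS figure is the all-patient rate and the mFAS figure is close to the as-observed rate, so the comparison one would want is already planned. A reader might infer from 8.2.3 alone that FAS and mFAS can never differ on any post-baseline outcome. The documents do not support that for binary endpoints while 8.1 stands. The reply does not settle the matter, though. The entry in 8.2.3 is made endpoint by endpoint and 8.1 is a general convention, so 8.2.3 is the more natural rule to follow, and nothing in the SAP gives precedence to either.

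A reader might also infer that the plan conceals the loss. It does not. SAP 7 requires missing counts for categorical variables and numbers of available observations for interval-scaled ones, and 8.1 adds missing counts for numerical data. Someone with those counts and the set sizes could work out R/N. Under 8.2.3 what is absent is a planned analysis that shows the effect on the rate.

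Three further points stand in part. The study is single-arm and descriptive, and the as-observed limitation is disclosed. Because visits follow routine practice, a missing Month 3 value may reflect scheduling, so counting it as non-response gives a one-sided bound. And the trigger may never be met.

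**Conclusion.** The point holds in a limited form. If 8.2.3 governs, the mFAS analysis reproduces the FAS Month 3 rates exactly, and this is an identity that needs no assumption about rates. For numerical post-baseline scores the two sets agree under any rule. If 8.1 governs, the binary rates differ, and the SAP then contradicts itself on the denominator of both primary endpoints. At an assumed 10% loss, with everyone else seen at Month 3, the gap between the two FAS rates is 3 to 7 points for observed response of about 30% to 70%. At 20% loss and 50% response it is 10 points.

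Under 8.2.3 no planned analysis, including the PP set, shows how far early loss could move the primary rates. At 10% loss and about 50% observed response, the all-FAS range is 45.1% to 55.1%. Every magnitude here is hypothetical, because the documents give neither a loss rate nor a response rate. The as-observed rate remains a legitimate descriptive summary; the weaknesses are an unclear denominator and a triggered analysis that adds nothing under the endpoint-specific rule.

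**What to change.** In SAP 5.3, 8.1 and 8.2.3:

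1. State one denominator for the Month 3 IGA 0/1 and EASI-75 rates: patients with an evaluable Month 3 value, with that n printed. Say that the missing category in 8.1 is a displayed count that does not enter this percentage.
2. Drop the mFAS for post-baseline scores.
3. In its place, at the same 10% trigger or always, report both Month 3 rates with every FAS patient in the denominator and no Month 3 value counted as non-response. Label it a sensitivity bound and set it beside the as-observed rate. The opposite bound, with missing counted as response, may be added so that the range is two-sided.
4. Report the number of FAS patients with no post-baseline visit.

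The cost is SAP wording and one table in place of another, with no new data. The drawback is that a less favourable, one-sided figure appears next to the main rate. Since some missing values may only reflect routine scheduling, the label should make clear that it is a bound and not an estimate.

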9.2.3.2. Schedule of Activities

The recommended schedule of activities table provides an overview of the visits that may be documented. Refer to Section 9.2.4 Assessments section of the protocol for detailed information on each documentation and assessment. As this is a non-interventional study none of these visits are mandatory and every visit should be scheduled according to clinical practice. According to clinical practice the HCP may schedule additional visits to those listed on the schedule of activities, in order to conduct evaluations or assessments required to protect the well-being of the patient.

Table 1. Recommended Schedule of Activities

Study period based on	Baseline	Month	Month	Month	Month	Month
routine visits	(Enroll ment)	1	3	6	9	12 End of Study (EoS)
Visit Number	1	2	3	4	5	6
Informed consent	X					
Inclusion/exclusion criteria	X					
Demographic data of patient (age, sex, weight, height, ethnicity, smoker/non- smoker, education, occupation, alcohol consumption, insurance type)	X					
Family history of atopic diseases	X					
Clinical history (Herpes simplex, eczema herpeticum, herpes zoster)	X					
Renal and/or liver impairment	X					
Vaccination status (Herpes zoster, Covid-19, Influenza, Varicella)	X					X
Age at initial diagnosis of AD	X					
Previous treatments for diagnosed AD	X					
Current comorbidities of interest (atopic diseases, malignancies, cardiovascular diseases)	X					
If positive anamnesis at baseline exists: Improvement of asthma symptoms from baseline						X

Study period based on routine visits	Baseline (Enroll ment)	Month 1	Month 3	Month 6	Month 9	Month 12 End of Study (EoS)
If positive anamnesis at baseline exists: Improvement of allergic rhinitis symptoms from baseline						X
If positive anamnesis at baseline exists: Improvement of polyposis nasi symptoms from baseline						X
If positive anamnesis at baseline exists: Improvement of alopecia areata from baseline						X
If positive anamnesis at baseline exists: Improvement of prurigo nodularis from baseline						X
If positive anamnesis at baseline exists: Improvement of hand eczema from baseline						X
Number of flares during the last 12 months (first visit) and since the last visit (regardless of Abrocitinib treatment status*)	X	X	X	X	X	X
Number of hospitalizations due to AD during the last 12 months (first visit) and since the last visit (regardless of Abrocitinib treatment status*)	X	X	X	X	X	X

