3 FINAL ANALYSES

The final analysis will include all enrolled patients and will be carried out after all patients have reached their final visit (at Month 12). The final datasets will be extracted from the database and locked before final analysis. Any exclusions from the analysis will be agreed and documented prior to database lock.

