6.1 EFFICACY/EFFECTIVENESS ENDPOINT(S)

Effectiveness endpoints comprise of all primary and secondary endpoints, i.e. effectiveness, and quality parameters assessed by the physicians and the patients.

Primary endpoint analysis

Variable	Role	Data source(s)	Operational definition
EASI	Primary outcome variable	Case records	Percentage of patients with 75% reduction from baseline in EASI at month 3
IGA	Primary outcome variable	Case records	Percentage of patients with IGA score 0 or 1 at month 3

Secondary endpoint analysis

Variable	Role	Data source(s)	Operational definition
SCORAD	Secondary outcome variable	Case records	Summary statistics (n, mean, median, standard deviation, minimum and maximum) of the total score and SCORAD-A at each point in time, respectively as well as the respective percentage change to baseline
EASI	Secondary outcome variable	Case records	 Percentage of patients with 75% reduction from baseline in EASI irrespective of the point in time Percentage of patients with 90% reduction from baseline in EASI irrespective of the point in time Summary statistics (n, mean, median, standard deviation, minimum and maximum) of the score at each point in time as well as the respective percentage change to baseline
IGA	Secondary outcome variable	Case records	 Percentage of patients with IGA score 0 or 1 irrespective of the point in time Percentage of patients with IGA score 0 or 1 and a reduction from baseline of ≥2 points irrespective of the point in time Summary statistics (n, mean, median, standard deviation, minimum and maximum) of the score at each point in time as well as the respective percentage change to baseline ((score at respective visit – score at baseline)/score at baseline*100)

Pruritus- NRS	Secondary outcome variable	Case records	Percentage of patients achieving at least 4 points improvement of Pruritus NRS from baseline Summary statistics (n, mean, median, standard deviation, minimum and maximum) of the score at each point in time as well as the percentage change to baseline Percentage of patients with Pruritus NRS ≤1
PP- NRS	Secondary outcome variable	Case records	 Percentage of patients achieving at least 4 points improvement of PP NRS from baseline Summary statistics (n, mean, median, standard deviation, minimum and maximum) of the score at each point in time as well as the percentage change to baseline Percentage of patients with PP NRS ≤1

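### The Per Protocol set requires every visit to Month 12, so the Month 3 primary endpoints are analysed in patients selected on attendance after Month 3

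*SAP*

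**What the plan says.** SAP 5.3 defines PP as patients who met the eligibility criteria, received at least one dose and "completed all visits, irrespective of the time-window". On its use, the section says "This population will be used for analysis of primary and secondary endpoints, if" at least 10% of the modified FAS (mFAS) is omitted. The summary table in SAP 8.2.3 lists FAS, mFAS and PP for both primary endpoints and does not repeat that condition.

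The two primary endpoints in SAP 6.1 are "Percentage of patients with IGA score 0 or 1 at month 3" and "Percentage of patients with 75% reduction from baseline in EASI at month 3". Month 3 is Visit 3.

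On follow-up, SAP 1.1 states: "The planned observation period of each patient is 12 months. In this time period up to 6 visits will be documented". The schedule has visits at baseline and Months 1, 3, 6, 9 and 12. Protocol 9.2.3.2 adds: "As this is a non-interventional study none of these visits are mandatory".

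On the FAS, SAP 5.1 says "This population will be used for all analyses except safety".

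**The concern.** A patient with a documented baseline, Month 1 and Month 3 visit has everything the primary endpoints need. If the Month 6, 9 or 12 visit is then not documented, SAP 5.3 removes that patient from the PP analysis of Month 3. This conditions the analysis on events that follow the outcome and may depend on it.

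Nor does the set measure adherence. Missing a visit is not a deviation when no visit is mandatory, and nothing in the definition concerns taking abrocitinib. Protocol 9.1 keeps patients who switch therapy under observation, and Protocol 10.3 says that stopping treatment is not withdrawal. A patient who switched before Month 3 but attended everything is in PP; an adherent patient who skipped Month 9 is out.

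At stake is the use of PP as a supporting analysis. Agreement or disagreement between PP and FAS at Month 3 could reflect later attendance alone, so neither could be read as a check on the FAS result.

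**Working it through.** The plan states no attendance rate, dropout rate or expected response, and Protocol 9.5 says a formal sample size calculation does not apply. There is no figure to reproduce. The structural point follows from the text; the arithmetic only shows scale, on assumptions.

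**Structure.** PP membership requires Visits 1 to 6. SAP 5.3 does not number the visits, but the schedule supports no other reading. The primary endpoints need Visits 1 and 3. No endpoint-specific PP definition appears elsewhere in the SAP. Membership for a Month 3 analysis therefore depends on Visits 4, 5 and 6.

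**Size of bias.** Take patients who completed Visits 1 to 3. Let *p* be their Month 3 response, and *a* and *b* the probabilities that responders and non-responders complete Visits 4 to 6 (all assumed). Then

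PP response = *pa* / (*pa* + (1 − *p*)*b*).

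Example: *p* = 0.50, *a* = 0.80, *b* = 0.60 gives 0.40 / (0.40 + 0.30) = 0.571.

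| Completion, responders / non-responders | *p* = 30% | *p* = 50% | *p* = 70% |
|---|---|---|---|
| 80% / 80% | 30.0% (0) | 50.0% (0) | 70.0% (0) |
| 80% / 70% | 32.9% (+2.9) | 53.3% (+3.3) | 72.7% (+2.7) |
| 80% / 60% | 36.4% (+6.4) | 57.1% (+7.1) | 75.7% (+5.7) |
| 70% / 80% | 27.3% (−2.7) | 46.7% (−3.3) | 67.1% (−2.9) |
| 60% / 80% | 24.3% (−5.7) | 42.9% (−7.1) | 63.6% (−6.4) |

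For comparison, if all 750 planned patients had a Month 3 outcome, the 80% / 60% row would leave about 495 to 555 in PP, with a 95% confidence half-width of about 3.6 to 4.3 points. A moderate difference in attendance can exceed sampling error.

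**When the 10% condition is met.** Assume each of the five post-baseline visits is documented independently with probability *q*. The PP share is *q*⁵, the mFAS share is 1 − (1 − *q*)⁵, and the share of mFAS omitted is 1 − *q*⁵ / [1 − (1 − *q*)⁵]. This reaches 10% once *q* falls below about 97.9%. With 750 patients, and comparing a rule that requires only Visits 1 to 3 (PP share *q*²):

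| *q* | PP now (mFAS omitted) | PP with Visits 1 to 3 (mFAS omitted) |
|---|---|---|
| 97% | 644 (14.1%) | 706 (5.9%) |
| 95% | 580 (22.6%) | 677 (9.7%) |
| 90% | 443 (41.0%) | 608 (19.0%) |

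Attendance usually clusters within patients, which would raise the PP share at a given *q*, so these omitted shares are on the high side. Even so, with optional visits the condition is likely to be met.

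**The case against.** Four points can be made for the plan.

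*The FAS is always reported, and the study is descriptive.* This stands. SAP 5.1 guarantees an FAS result for both primary endpoints, and SAP 4 sets no hypotheses or decision rules, so no conclusion hangs on PP alone. It limits the consequence but does not repair the PP figure, and the SAP does not say which set leads.

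*PP is conditional.* SAP 5.3 brings it in only when at least 10% of the mFAS is omitted. But that is exactly when most patients are removed and selection has most room to act, and SAP 8.2.3 lists PP without the condition.

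*A 12-month completer cohort has a use.* It keeps one denominator across visits for the longitudinal secondary endpoints. That is fair, but it does not justify the set for Month 3.

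*A PP set tied to Month 3 would nearly duplicate the FAS.* Largely true if missing data are excluded, as SAP 8.2.3 says; less so if missing counts as a category, as SAP 8.1 says. It is a reason to require all visits up to the endpoint's own visit, and not merely a Month 3 assessment.

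A reader might also infer that ignoring the time window lets an out-of-window assessment count as Month 3. The documents do not support this. The phrase governs membership only; SAP 1.1 and SAP 6 assign values to Month 3 by study day. Under the amended windows a visit on day 110 falls in the Month 6 slot (days 106 to 210), not Month 3 (days 45 to 105).

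**Conclusion.** The point holds as a flaw in the definition of a supporting analysis set. As written, the SAP discards observed Month 3 outcomes because of later non-attendance, and no other section corrects this.

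A reader might go further and conclude that the PP rate will be inflated. The documents do not support that. Selection is on documented visits, not on staying on treatment; patients who stop or switch remain under observation, and well-controlled patients may be the ones who attend less. Bias is upward, downward or zero according to how attendance at Visits 4 to 6 relates to Month 3 response, and nothing in either document fixes this. The figures of about 3 points (80% against 70%) and 6 to 7 points (80% against 60%) are illustrations on assumed completion rates, with equal and opposite possibilities. What can be said without assumptions is that a Month 3 comparison of PP with FAS cannot be interpreted as intended.

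**What to change.** In SAP 5.3, define PP per endpoint: eligible, at least one dose, and all visits completed up to and including the endpoint's own visit (Visits 1 to 3 for the Month 3 endpoints), with no condition on later visits. Selection on events after Month 3 is then removed by construction.

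If a 12-month completer cohort is wanted for the longitudinal secondary endpoints, define it separately under that name and do not apply it to the Month 3 primary endpoints.

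Name FAS as the lead set. State whether PP is run always or only when at least 10% of the mFAS is omitted, and make 5.3 and 8.2.3 agree.

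The cost is SAP wording, with no new data. PP becomes larger. The downside is that the Month 3 PP result will lie closer to the FAS observed-case result and so add less, and if the 10% condition is kept it will be met less often (9.7% omitted at *q* = 95% in the table above).
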